EVCTM	EudraVigilance Clinical Trial Module
e.g.	exempli gratia
GCP	Good Clinical Practise
GDHT	Goal Directed Hemodynamic Therapy
GOS	Glasgow Outcome Scale
HR	Heart Rate
ICF	Informed Consent Form
ICH E6	harmonized guideline for good clinical practise
ICU	Intensive Care Unit
ICU LOS	Intensive Care Unit Length of Stay
i.e.	id est
IMP	Investigational Medicinal Product
i.v.	intravenous
KDIGO	Kidney Disease Improving Global Outcomes
LOS	hospital length of stay
MAP	Mean Arterial Pressure
MedDRA	Medical Dictionary for Regulatory Activities
MRI	Magnetic Resonance Imaging
NMBA	neuromuscular blocking agent
OR	odds ratio
PE	Pulmonary Embolism
PEEP	Positive End-Expiratory Pressure
RBC	red blood cells
SADR	Serious Adverse Drug Reaction
SAE	Serious Adverse Event
SAP	Statistical Analysis Plan

SBP	Systolic Blood Pressure
SmPC	Summary of Product Characteristics
SpO2	Saturation of Peripheral Oxygen
SUSAR	Suspected Unexpected Serious Adverse Reaction
SV	Stroke Volume
SVI	Stroke Volume Index
SVV	Stroke Volume Variation
TCI	Target Controlled Infusion
TFC	Thoracic Fluid Content
TIVA	Total Intravenous Anaesthesia
TPR	Total Peripheral Resistance
TPRI	Total Peripheral Resistance Index
UADR	Unexpected Adverse Drug Reaction
VET	Ventricular Ejection Time

1. CLINICAL TRIAL BACKGROUND

1.1. Goal-directed hemodynamic therapy (GDHT)

Goal-directed hemodynamic therapy (GDHT) is a complex group of interventions aimed at improving oxygen delivery and tissue perfusion, successfully used in several surgical indications during perioperative period. Many devices - from invasive to minimally invasive - can be used to determinate various hemodynamic values, which can be targeted to predefined goals through titration of intravenous fluid and vasoactive drugs [1]. GDHT has been shown to reduce postoperative complications (e.g. acute kidney disease, pulmonary oedema, wound infection) and decrease hospital length of stay in patients undergoing major abdominal, urological, gynecological and orthopedic procedures [2,3].

Due to the wide application of this methodology in surgery, several meta-analyses processing data from clinical trials have been published in the last decade. Jessen et al. [4] identified 76 comparative studies in which GDHT protocols including fluid therapy to optimize stroke volume (or related parameter) were compared with standard care. Analysis of data from 9081 patients undergoing non-cardiac surgery showed a moderate-certainty-of-evidence reduction in postoperative pneumonia, surgical site infection and anastomotic leakage in the GDHT arms, while effects on mortality and hospital length of stay were not demonstrated.

A systematic review to assess the effect of GDHT exclusively on post-operative pulmonary complications in patients undergoing surgery performed Dushianthan et al. [5]. A significant reduction in total pulmonary complications (OR 0.74, 95% CI 0.59 to 0.92) in GDHT group was demonstrated in a sample of 9548 participants (66 studies in total). Meta-analysis suggests that the use of GDHT using fluids with inotropes and/or vasopressors, but not fluids alone, reduces the development of post-operative pulmonary infections and pulmonary oedema in patients undergoing abdominal and cardiothoracic surgery. The pitfalls of meta-analyses focusing on GDHT in general, such as the clinical heterogeneity of patients, interventions and outcomes, are pointed out in the review by Kaufmann et al. [6]. Saugel et al. [7] recommend consistently including only trials using similar perioperative hemodynamic treatment strategies (hemodynamic target variables, target values, and triggered interventions) in meta-analyses to avoid oversimplification that could lead to incorrect conclusions.

1.2. GDHT in neurosurgical interventions

Patients undergoing major neurosurgery are at risk for inadequate intravascular volumes. Fluid overload can contribute to worsening brain oedema. On the other hand, the administration of diuretics to reduce brain oedema, reduction of preoperative fluid intake, and intraoperative blood loss leads to a decrease in intravascular volume and thus to a decrease in blood flow and oxygen supply to the brain and other tissues, resulting in organ dysfunction. The use of goal-directed hemodynamic therapy (GDHT) guided by non-invasive measurement of hemodynamic parameters aims to optimize the intravascular volume, thereby improve blood flow through tissues and reduction of the incidence of postoperative adverse events.

1.2.1. Spine surgery

In contrast to the surgical fields mentioned above, only limited data are currently available on the GDHT efficacy in neurosurgery. For spine surgery in the prone position, conflicting results from several monocentric studies are available. Picard et al. [8] confirmed that intraoperative use of esophageal Doppler and optimization of perioperative fluid management is feasible and may help to reduce the duration of hypotensive episodes during spinal surgical procedures. Conversely, a study by Wongtangman et al. [9], despite similar clinical characteristics, did not demonstrate significant benefits of the GDHT protocol with respect to intraoperative hypotension, blood transfusion, or postoperative complications in patients undergoing complex spine surgery. Results published by Abdelhamid et al. also failed to demonstrate a benefit of the GDHT compared to conventional fluid management in 66 adult patients undergoing spine surgery. The goal-directed fluid management therapy dependent on plethysmographic variability index did not reduce the intraoperative total crystalloid administration or requirements for blood transfusion [10].

Maintainance of targed levels of mean arterial pressure (MAP) and stroke volume (SV) through fluid therapy and vasopressor administration with minimally invasive hemodynamic monitoring was used by Andrzejewska et al. in a prospective pediatric case-control study in elective scoliosis surgery [11]. The GDHT group (n=24, mean age 14 years) showed a significantly shorter duration of hypotension (mean arterial pressure < 60 mmHg), reduced hospital stays, smaller decreases in postoperative hemoglobin levels and shorter times from the end of surgery to extubation.

1.2.2. Brain surgery

A study investigating the effects of a GDHT strategy in patients undergoing high-risk brain surgery (GDHT group [n=73] vs. control group [n=72]) where appropriate fluid management is necessary due to impending brain oedema was conducted by Luo et al. [12]. According to published results, ICU length of stay was shorter (3 days [1–5] vs. 6 days [3–11], $p = 0.001$) and ICU costs were lower in the GDHT group. The total number of complications (46 vs. 99, $p = 0.043$) and the proportion of patients who developed one or more complications (19.2 vs. 34.7%, $p = 0.034$) were less in the GDHT group compared to patients who received standard care.

The ability of the GDHT approach compared with standard clinical care to reduce the rate of delayed cerebral ischemia (DCI) after subarachnoid hemorrhage was investigated by Anetsberger et al. [13] in a prospective randomized controlled trial with 108 adult subjects. The primary outcome (DCI) occurred in 13% of patients in the GDHT group (n=54) and in 32% of patients in the control group (n=54). Moreover, reduced rate of DCI was associated with a better functional outcome (GOS=5) 3 months after discharge.

Another study [14] was designed to assess the influences of arterial pressure continuous output (APCO) derived SVV-guided fluid management on postoperative complications and outcome in patients undergoing supratentorial neoplasms surgery. Based on data obtained from 66 patients, SVV-guided fluid management was associated with a lower incidence of postoperative complications and did not induce additional risk of brain oedema (degree of brain oedema 1 day postoperatively did not differ between study groups [3 vs. 3, $P=0.96$]).

Finally, a study conducted in 48 patients scheduled for elective craniotomy was designed to test whether intraoperative goal-directed fluid management using SVV-guided 0.9% normal saline administration could alleviate metabolic acidosis compared with CVP-based fluid administration. Contrary to the hypothesis, intraoperative targeted fluid therapy based on SVV values from the FloTrac/Vigileo™ system did not reduce the severity of metabolic acidosis in patients undergoing brain tumor resection compared with CVP-guided fluid therapy [15].

1.3. The Starling™ SV System

The Starling™ SV System is a portable, non-invasive cardiac output (CO) monitoring device based on BIOREACTANCE® technology that is capable of predicting response to intravenous fluids in critical care situations similar to invasive methods (e.g. esophageal Doppler). It also measures heart rate (HR), stroke volume (SV), stroke volume variation (SVV), ventricular ejection time (VET), mean arterial pressure (MAP), systolic blood pressure (SBP), diastolic blood pressure (DBP), saturation of peripheral oxygen (SpO2) and thoracic fluid content (TFC). In addition, the system calculates some other clinical parameters such as cardiac index (Cl^a), stroke volume index (SVI), total peripheral resistance (TPR), total peripheral resistance index (TPRI), cardiac power (CP), cardiac power index (CPI) or oxygen delivery index (DO2I). The Starling™ SV System is registered in the Registry of Medicinal Devices under reference number [00538564](#) and is not subject to the obligation of any clinical tests of the medical device in this clinical trial. Only limited data have been published on its use in neurosurgery [16], the expansion of this knowledge is one of the goals of this clinical trial.

1.4. Study rationale

Surgical procedures, particularly in neurosurgery, pose significant challenges in fluid management. The balance between maintaining adequate intravascular volume to ensure sufficient organ perfusion while avoiding fluid overload is crucial for optimizing patient outcomes. Neurosurgical patients face unique factors contributing to fluid imbalance, including preoperative diuretic use, decreased oral intake, and the risk of intraoperative blood loss. These factors can lead to hypovolemia, compromising organ perfusion and increasing the risk of complications. Conversely, excessive fluid administration can exacerbate issues like cerebral edema and compromise cardiac function.

The goal-directed hemodynamic therapy (GDHT) approach has shown promise in various surgical subspecialties, demonstrating reductions in perioperative complications, shorter hospital stays, and decreased costs. However, its application in neurosurgery remains understudied. The primary aim of this study is to determine whether optimizing fluid management during elective neurosurgical procedures reduces the occurrence of postoperative adverse events in adult patients compared to standard care.

1.5. Anticipated risks and benefits

The feasibility and safety of a GDHT approach using the non-invasive Starling™ SV System in neurosurgery was evaluated in a pilot study (34 adult subjects). No patient had unsatisfactory relaxation of brain tissue after surgery or brain oedema requiring therapy during surgery or 24 hours after surgery. Major complications occurred in two (11.8 %) patients in the

GDHT group and six (35.3%) patients in the control group ($p = 0.105$) [17]. The Starling™ SV System is an approved medical device, which will be used in accordance with its stated purpose and manufacturer's recommendations. As part of this clinical trial, only registered medicinal products that are standardly used in the given indication will be used, so there is no assumption of the emergence of new safety signals resulting from the use of these products.

The clinical outcome of an individual participant in this trial may or may not be improved. If effective, GDHT might help to optimize intravascular volume, prevent fluid overload or hypovolemia and thereby reduce the incidence of postoperative adverse events in adult patients undergoing elective neurosurgery. As elective neurosurgical procedures are generally high-risk, all participants in this clinical trial will be provided with proper peri- and post-operative care and immediate medical attention will be provided in case of any unexpected events.

2. TRIAL OBJECTIVES AND ENDPOINTS

2.1. Aim of the study

This study aims to assess the safety and efficacy of GDHT using the non-invasive Starling™ SV System in elective neurosurgery. The tested group of patients (n=70) will be compared with a control group (n=70), where hemodynamic management will be guided by standard vital signs monitoring.

2.2. Primary objective(s) and endpoint(s)

The **primary objective** of the clinical trial is to determine the effect of GDHT guided by the non-invasive Starling™ SV System on the incidence of postoperative complications in patients undergoing neurosurgical intervention.

The following **primary endpoints** will be monitored to evaluate the primary objective:

1.) Incidence of adverse events and reactions according to following Adverse Events of Special Interest (AESI) in both study groups.

Monitored parameters (AESI): (YES/NO)

Detailed **definitions and grading** of individual **AESI** can be found in **Appendix A 14.1**

- Acute Kidney Injury (stage 2, 3 according to KDIGO guidelines)
- Acute Respiratory Distress Syndrome (ARDS, according to Berlin definition of Respiratory Distress Syndrome)
- Arrhythmia (moderate/severe)
- Cardiac arrest
- Cardiogenic pulmonary oedema (moderate/severe)
- Deep vein thrombosis (DVT; moderate/severe)
- Pulmonary embolism (PE)
- Gastrointestinal bleed (moderate/severe)
- Infection, source uncertain (moderate/severe)
- Laboratory confirmed bloodstream infection (moderate/severe)
- Myocardial infarction (moderate/severe)
- Pneumonia (moderate/severe)
- Paralytic ileus (moderate/severe)
- Postoperative haemorrhage (moderate/severe)
- Stroke (moderate/severe)
- Brain oedema (CT or MRI proven; moderate/severe)
- Surgical site infection (superficial; moderate/severe)
- Surgical site infection (deep; moderate/severe)
- Surgical site infection (organ/space; moderate/severe)
- Urinary tract infection (moderate/severe)

2.3. Secondary objective(s) and endpoint(s)

The **secondary objective** is to investigate the efficacy and additional safety parameters of GDHT guided by non-invasive advanced hemodynamic monitoring versus hemodynamic management guided by standard vital signs monitoring.

Secondary endpoints are as follows:

1.) Additional safety information

Monitored parameters:

- Duration of surgery (min)
- LOS (day of admission – day of discharge will be counted as 1 day)
- ICU LOS (day of admission – day of discharge will be counted as 1 day)
- 28-day mortality (number of patients who are not alive 28 days after randomization)
- Descriptive analysis of the incidence of any adverse events and reactions

2.) Comparison of hemodynamic characteristics and their changes over time between study groups

Monitored parameters:

- MAP (mmHg; before, after surgery)
- HR (Bpm; before, after surgery)
- SVV (%; before, after surgery)
- Number of episodes of hypotension¹
- Number of vasopressor administrations

3.) Comparison of laboratory values of selected blood parameters and their changes over time between study groups

Monitored parameters:

- Hemoglobin (g/l; before, after surgery and 24 hours after surgery)
- Plasma lactate level (mmol/L; before, after surgery and 24 hours after surgery)

4.) Comparison of fluid balance and fluid therapy between study groups

Monitored parameters:

- Volume of blood loss (ml/kg; during surgery² and in the 24-hour postoperative period)
- Urinary output (ml/kg/hod; during surgery² and in the 24-hour postoperative period)
- Number of administered units of packed RBC (during surgery² and in the 24-hour postoperative period)

¹ MAP bellow 65 torrs [18]

² **duration of surgery** is considered as the time from the skin incision to the suture of the dura

- Number of subjects receiving transfusion (during surgery² and in the 24-hour postoperative period)
- Crystalloid and colloid solutions consumption (type and total volume of infusion during surgery² and in the 24-hour postoperative period)
- Boluses of crystalloids (ml; during surgery²)

3. TRIAL DESIGN

The **NCHGDT** is a multicenter, prospective, randomized, controlled trial comparing the efficacy and safety of two approaches to fluid management in elective neurosurgery; GDHT guided by the non-invasive Starling™ SV System versus hemodynamic management guided by standard vital signs monitoring. The study will be conducted at the University Hospital Brno, Czech Republic and in other Czech centers that have appropriate equipment for advanced hemodynamic monitoring. Optimal standard treatment will be achieved in both arms of the study using the current best treatment protocol. The anticipated sample size is 140 patients randomized into study groups in a 1:1 allocation ratio and followed up for 28 days after surgery. End of study is defined as the time of completion of the 28-day follow-up in the last patient. The expected duration of this clinical trial is 3 years.

4. TRIAL POPULATION

4.1. Inclusion criteria

Subjects will **be eligible** for the trial if they **meet all** of the following **criteria**:

1. Age \geq 18 years
2. Elective brain surgery with an expected duration \geq 2 h
3. Category 1-3 according to the ASA Physical Status Classification
4. Lateral or supine operative position
5. Signed the relevant informed consent form (more in Chapter 10.1)

4.2. Exclusion criteria

Subjects will **not be eligible** for the trial if they **meet any** of the following **criteria**:

1. Category 4 according to the ASA Physical Status Classification
2. Surgery for traumatic brain injury or acute hemorrhagic stroke
3. Awake brain surgery
4. Osmotherapy before surgery (with the exception of prophylactic administration of osmotic agents according to institutional standards)
5. Unavailability of hemodynamic monitoring data
6. Cardiac arrhythmia with irregular cardiac rhythm
7. Known hypersensitivity to the active substance or to any of the excipients of IMP (see Chapter 5)
8. Pregnancy and lactation

4.3. Randomization

Participants will be randomized in a 1:1 ratio to the two study arms (GDHT or STANDARD) using the eCRF REDCap database shortly before surgery by a member of the study team.

4.4. Blinding

The neurosurgeon, ICU staff and members of the study team collecting data will be blinded. The hemodynamic monitor will be placed in the operating room during all study interventions so that the neurosurgeon cannot see whether it is being used or not. Other study staff and attending physicians and other staff will not be blinded, as blinding is not possible when conducting the study intervention. The data management group and statisticians will work with a pseudo-anonymized data set.

4.5. Enrolment stopping rules

Enrolment of new subjects into the trial may be stopped in situations that could lead to an immediate risk to patients (e.g. epidemics of serious infectious diseases, etc.) or if a new toxicity of the study medication is newly identified.

4.6. Premature termination of participation in the trial

Reasons for early termination of a patient's participation include:

- Withdrawal of informed consent (subject's decision to withdraw for any reason);
- Important deviation in the process of informed consent (Chapter 10);
- Life-threatening adverse reaction related with IMP or study intervention at the discretion of the investigator;
- Pulmonary oedema or cardiac decompensation is suspected;
- Newly-emerged pregnancy of a participant after the enrolment;

Subjects **can terminate their participation prematurely** at any time at their request for any reason, but they must notify the investigator. The investigator must contact the sponsor to report the premature discontinuation.

The investigator must:

- Instruct the participant about the right on early termination of participation;
- Assure him/her that the end of participation will not affect the attitude of the physician, or further treatment and its quality;
- Ask for discussing this decision with the investigator in advance;
- Make a note in the patient's medical records and eCRF about the date of early termination of participation.

The **sponsor** reserves the **right to discontinue the study** at any time if there is a significant safety concern, or insufficient recruitment despite intensified efforts to enrol patients, or if repeated poor study documentation occurs at a site. The trial can be discontinued by the decision of the **regulatory authority** or **ethics committee**, as well.

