6.2. Clinical examinations and assessments

During the trial course, subjects will be monitored during hospitalization and after discharge. A summary of scheduled procedures is outlined in Chapter 6.3. For a graphic summary see Table 1.

Table 1: Clinical trial schedule

	STUDY PERIOD						
	Screening	Allocation	Post-allocation		Hospital discharge	Follow-up	Premature termination
TIMEPOINT	D ₋₃₋₀		D ₁	D ₂	D ₃₋₂₈	D ₂₈	Anytime
ENROLMENT:							
Eligibility criteria	X						
Informed consent	X						
Pregnancy testing ¹	X						
Randomization		X					
ASSESSMENTS:							
Demographic data ²		X					
Fluid therapy ³			X	X			
Laboratory testing ⁴			X	X			
Hemodynamics ⁵			X	X*			
Adverse events			X	X	X	X	X
Postoperative complications (AESI ⁶)			X	X	X	X	X
Blood loss ⁷			X	X			
Urinary output ⁸			X	X			
Transfusion products consumption ⁹			X	X			
Duration of surgery (min)			X				
ICU LOS (days)					X		
LOS (days)					X		
28-day mortality						X	
Reason for premature termination							X

1 urine pregnancy testing

2 age, sex, weight

3 type and volume (ml) during surgery and in the 24-hour postoperative period (for more details see Chapter 2.3, point 4.)

4 hemoglobin, plasma lactate level (for more details see Chapter 2.3, point 3.)

5 MAP, HR, SVV, number of hypotension episodes, number of vasopressor administrations (for more details see Chapter 2.3, point 2.)

6 for more details see Chapter 2.2

7 volume (ml/kg) during surgery and in the 24-hour postoperative period

8 volume (ml/kg/hod) during surgery and in the 24-hour postoperative period

9 number of administered units of packed RBC during surgery and in the 24-hour postoperative period

*except SVV

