- Monitoring of hemodynamic parameters except SVV
- Monitoring of adverse events and reactions including postoperative complications of special interest

Day 3 to Day 28 / ICU discharge (whichever comes first)

- Checking adverse events and adverse reactions (with special interest in postoperative complications of special interest)
- Discharge from ICU and hospital

Day 28

- Checking adverse events and adverse reactions (outpatient or telephone call)
- Mortality assessment

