7.2. AE surveillance, recording and documentation

AE could be diseases or symptoms which occur or worsen after the enrolment of a patient in the clinical trial. All AEs need to be documented, no matter if the investigator suspects a causal

connection to the study medication. AE will be monitored and documented **from the day of giving informed consent until the end of participation in the study** (i.e., End of Study Visit or Premature withdrawal Visit).

Subjects will be instructed to report any AEs that they experience to the investigator. The investigator should actively ask about AEs and record the potential AE.

Each AE should be described, documented in the eCRF, and evaluated to determine:

- Seriousness (see Chapter 7.4);
- Severity (see Chapter 7.5);
- Causality, i.e. relation to the study medication (see Chapter 7.6);
- Duration (start and end dates or whether it continues).
- Action taken (no action taken; study medication discontinued; prolongation of the ongoing hospitalization; administration of a drug etc.)

AE needs to be **followed until its resolution**, i.e. until it subsides, stabilizes, becomes chronic, or the subject dies.

If AE fulfils the criteria of **SAE**, **separate form in eCRF** must be completed (see Chapter 7.7).

AEs will be recorded according to the Medical Dictionary for Regulatory Activities (MedDRA). The most recent MedDRA version at the start of the study will be used.

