7.7. Reporting of SAE and SUSAR

The investigator is obliged to report any SAE within 24 hours after he/she learns about it to the sponsor using Serious Adverse Event Form (SAE Form). The blank forms are stored in the Investigator's Site File. Reporting should be done by e-mail: [contact] AND [contact].

Sponsor will check the SAE Form completeness and formal plausibility. If required, queries will be made.

If all required information is not available at the time of the initial SAE report, follow-up reports should be sent by the investigator. Follow-up report should use a new blank SAE Form and the investigator should clearly state that this is a follow-up and give the date of the initial report. The investigator must update the SAE form and submit any supporting documentation (e.g., lab results, subject discharge summary, autopsy report) within 24 hours of receipt of this new information. The follow-up SAE report should describe whether the event has resolved or continues, if and how it was treated and whether the patient continued or withdrew from trial participation.

All SAEs should be followed until their resolution, i.e., they subside, stabilize, become chronic, or the subject dies followed. In case of early termination because of SAE occurrence, the subject should be followed until SAE resolution. All necessary extra visits will be recorded in the eCRF as "Unscheduled visits".

In the case of death, a copy of the autopsy record should be added, if available. If the death of the subject complies with the definition of SUSAR (see Chapter 7.1), it will be reported as SUSAR (see below).

Sponsor has full responsibility for the safety of the clinical trial. Further reporting of AEs to the competent authorities according to the legal requirements is the responsibility of the sponsor.

Reporting of SUSAR

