8.6. Analysis sets

Full analysis set (FAS)

FAS comprises all randomized patients who underwent surgery. All endpoints will be evaluated using FAS.

Per-protocol set (PPS)

PPS includes all patients from FAS without protocol deviations which might affect the evaluation of primary endpoint. The principal investigator will assess protocol non-adherence on a case-by-case basis. Patients with significant deviations from the study protocol will be excluded from PPS.

PPS will be used for analysis of primary endpoint.

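### Suspected pulmonary oedema or cardiac decompensation ends trial participation rather than only the study intervention, so later complications, length of stay and Day-28 survival are not scheduled for these patients

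*Protocol*

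**What the plan says.** Protocol section 4.6 concerns the end of a patient's participation in the trial. Its list of reasons includes "Pulmonary oedema or cardiac decompensation is suspected", alongside withdrawal of consent, a serious flaw in the consent process, pregnancy, and "Life-threatening adverse reaction related with IMP or study intervention at the discretion of the investigator". It provides no category in which the intervention stops but follow-up continues.

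Four other places determine what is then collected:

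- **Section 7.2** records adverse events until participation ends, defined as "i.e., End of Study Visit or Premature withdrawal Visit". Events already recorded are followed to resolution.
- **Section 7.7** adds: "In case of early termination because of SAE occurrence, the subject should be followed until SAE resolution".
- **Table 1 (section 6.2)** marks adverse events, adverse events of special interest (AESIs) and the reason under premature termination. ICU and hospital length of stay are marked only at hospital discharge, and "28-day mortality" only at the Day-28 follow-up.
- **Section 8.6** keeps the patient in the main analysis: "FAS comprises all randomized patients who underwent surgery".

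Under section 8.5, missing data are in general not imputed, and duration endpoints missing because of premature discontinuation are excepted from the imputation rules.

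**The concern.** The analysis set calls for outcomes that the visit schedule stops collecting. The primary endpoint is the proportion of patients with any AESI, with follow-up to 28 days, and section 8.3 counts deaths to 28 days after randomization. A patient whose participation ends on Day 1 or 2 has no scheduled source for either result after that point.

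This loss is unlikely to be random. Fluid overload is what section 1.5 hopes goal-directed therapy (GDHT) will prevent, and moderate or severe cardiogenic pulmonary oedema is itself an AESI. The reason for leaving is thus tied both to the treatment comparison and to the endpoint. Suspicion is also a judgement, and section 4.4 says: "Other study staff and attending physicians and other staff will not be blinded". Suspicion raised during surgery can therefore be influenced by knowledge of the arm. ICU staff and data collectors are blinded, which limits this after surgery.

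The direction cannot be predicted. If GDHT prevents overload, more terminations fall in the STANDARD arm; if repeated boluses triggered by stroke volume variation cause it, more fall in the GDHT arm. Since section 8 describes all tests as exploratory, what is mainly at stake is the estimated difference and its 95% CI.

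**Working it through.** **1. Which outcomes are lost**

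| Outcome | Collected after termination for this reason? | Source |
|---|---|---|
| AESI up to and at the termination visit | Yes | Table 1 |
| Adverse event already recorded, or the SAE that led to termination | Yes, to resolution | 7.2, 7.7 |
| Confirmed moderate/severe cardiogenic oedema | Yes; the patient already counts as having an AESI | 2.2 |
| New, different AESI before Day 28 | No; recording has closed | 7.2 |
| ICU and hospital length of stay | Not scheduled | Table 1 |
| Vital status at Day 28 | Not scheduled; only a death from a followed event would be seen | Table 1, 7.2, 7.7 |

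For the primary endpoint the gap is therefore confined to patients whose suspected event proves mild, is not confirmed, or is decompensation without qualifying oedema, and who have no other AESI by termination. For length of stay and vital status it covers every patient terminated for this reason.

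**2. Inputs from section 8.1**

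70 patients per arm, AESI rates of 33% and 11%, two-sided 5% level, 80% power, 10% dropout included. A continuity-corrected two-proportion calculation gives 64 per arm, and 64/0.9 rounds up to 72, or 144 in total. Exact Fisher power reaches 80% at 62 per arm, and 62/0.9 rounds up to 69, or 138 in total. The stated 140 is thus reproduced approximately and is not affected by this point.

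Expected counts are 0.33 × 70 = 23.1 and 0.11 × 70 = 7.7, taken as 23 and 8.

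**3. Weight of one unseen event**

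1/70 = 1.4 percentage points in its arm.

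**4. Bias in one arm**

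The protocol gives no number of terminations for this reason. *Assumption:* k = 2 to 4 patients in one arm, with later AESI risk q = 11% to 33% (the design rates), the rest of the arm having risk p.

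- Counted as event-free, the arm is understated by k × q / 70. Smallest: 2 × 0.11 / 70 = 0.31 points. Largest: 4 × 0.33 / 70 = 1.89 points.
- Dropped from the denominator, the arm is understated by k × (q − p) / 70. This is 0 if q = p. With q = 0.33 and p = 0.11 it is 0.63 points at k = 2 and 1.26 points at k = 4.

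**5. Effect on the test**

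Suppose 23 against 8 is what is recorded, and further GDHT events went unseen:

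| STANDARD vs GDHT, of 70 each | Chi-square p | Fisher p |
|---|---|---|
| 23 vs 8 (none unseen) | 0.0023 | 0.0039 |
| 23 vs 10 (2 unseen) | 0.0096 | 0.0161 |
| 23 vs 11 (3 unseen) | 0.0180 | 0.0293 |
| 23 vs 12 (4 unseen) | 0.0318 | 0.0501 |
| 23 vs 13 (5 unseen) | 0.0531 | 0.0810 |

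Significance at 5% is lost with 4 unseen events (Fisher) or 5 (chi-square). At the assumed risks, 4 events would need about 4/0.33 = 12 terminated patients and 5 events up to 5/0.11 = 45, that is 17% to 65% of the arm. In the other direction, five STANDARD events lost and counted as absent (18 vs 8) still give p = 0.030 by chi-square and 0.049 by Fisher.

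**The case against.** The strongest reply is that the primary-endpoint gap needs several things to coincide: a suspicion that does not become a qualifying oedema, no other AESI by termination, and then a new one before Day 28. The assumed 2 to 4 patients imply only 2 × 0.11 = 0.2 to 4 × 0.33 = 1.3 unseen events, and nothing in the protocol supports even that number. This stands: the likely bias is small, and a reversed test result at the design rates is remote.

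It can also be said that the plan anticipates discontinuation, with a 10% dropout allowance in section 8.1 and a missing-data section that refers details to the SAP. That addresses power and handling. It does not address bias, and no analysis plan recovers outcomes that were never collected.

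A blank under premature termination in Table 1 may show only that an item is not assessed at that visit, since the definition of Day-28 mortality makes no exception for terminated patients. This is fair for mortality and length of stay, where the accurate statement is that they are not scheduled. For later AESIs, section 7.2 closes recording outright.

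Finally, GDHT is described only for the operation, so for a suspicion arising in the ICU there may be no intervention left to stop. That is true, but it strengthens the point: ending participation then mainly ends data collection.

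**Conclusion.** The concern holds. Followed as written, sections 4.6 and 7.2 and Table 1 stop outcome collection for patients who remain in the full analysis set, for a reason linked to the fluid strategy and to a component of the primary endpoint.

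The likely effect on the primary endpoint is small to moderate: 0 to 1.9 percentage points in one arm against a planned difference of 22. This rests on the assumed 2 to 4 terminations and later risks of 11% to 33%. The loss of Day-28 vital status and length of stay affects every such patient but cannot be sized from the protocol. The direction is unknown. The point should be fixed because the loss is plausibly informative and easily avoided.

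**What to change.** Reconcile sections 4.6 and 7.2 and the premature termination column of Table 1 as follows:

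- Distinguish discontinuation of the study intervention from the end of trial follow-up.
- Unless consent is withdrawn or invalid, continue collecting AESIs, other adverse events, discharge dates and vital status to Day 28 for every patient, using the outpatient or telephone contact already in section 6.3. This also covers the other non-consent reasons in section 4.6.
- State that these patients remain in the full analysis set with their Day-28 outcomes.

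Whether and when the intervention stops remains a clinical decision and is not part of this change. Section 8.5 need not be altered. A best-case/worst-case sensitivity analysis for any AESI status that remains unknown can go in the SAP.

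The cost is a wording amendment and one Day-28 contact, of an existing type, for each patient concerned. Their number is unknown.
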